10.6 DATA MANAGEMENT

CRO Team will be responsible for the eCRF data management after receipt the data from the Investigators.

Pharmacovigilance Team will be responsible for safety data collection, processing and reporting.

The study will utilize existing databases known as “patient clinical records”. Each database may have different processes for managing and extracting data, following the standard practices established by the respective study site.

Once the Investigators have re-transcribed the relevant data, it will be transferred to electronic-based case report form (CRF). To maintain patient confidentiality, a unique dummy study identification number (SIN) will be assigned to each enrolled patient before delivering the data to Corza Medical. Corza Medical will receive the data without any identifiable patient information. At Corza Medical, the SINs will be used for linking the data at an individual level. This means that the researchers at Corza Medical will have access to data where individuals cannot be directly identified. After receiving the data from the Investigators, Corza Medical, in cooperation with entities involved in conducting the study, will process the data.

Computer software will be utilized for data management, including creating the analysis database and performing statistical analyses to generate tables, graphics, and statistical models. An audit trail will be maintained, documenting the entire data processing journey from the raw data obtained from the study sites to the final statistical tables and graphs in the reports. The source code for data management and analysis will be retained for inspection for a period of 15 years after the end of the study. The study may be subject to inspection by independent representatives appointed by the Sponsor, EMA representatives, the scientific committee, or competent authorities.

10.7 DATA ANALYSIS

All analyses will be performed for the study population, which will comprise all enrolled subjects who received at least 1 application of TachoSil. Study endpoints will be summarised by descriptive statistics. For primary and secondary endpoints, rate of occurrence and cumulative incidence of AEs and AESIs will be determined. Time to onset (TTO), duration, severity, outcome, treatment and relatedness to TachoSil will be analyzed for reported AEs and AESI.

Descriptive statistics of all endpoints may include specifically but not exclusively, arithmetic mean, medians, standard deviations, proportions, frequency counts and 25th and 75th percentiles. Where applicable, 95% confidence intervals of select point estimates will be determined. Figures will be prepared to illustrate the patterns of data over time where appropriate. The number of subjects included in each analysis set will be reported.

A qualitative comparison of results collected during the study with an existing literature data will be performed, particularly focusing on the incidences, time to onset, severity, and outcomes of AESIs and SAEs, with existing literature. Literature searches in databases like PubMed, Embase and Cochrane Library will be conducted to identify relevant studies. The search will use specific keywords and criteria related to TachoSil, adverse events, and study

populations.- Studies selected for comparison will be based on relevance, quality, and up to date results. Key data from the selected studies, such as incidences, time to onset, severity, and outcomes of AESIs and SAEs, will be extracted. A standardized form will be used to ensure consistent data collection. A narrative synthesis will be provided, discussing similarities and differences in the findings. Both our study and the selected literature will undergo a critical appraisal to assess the quality and risk of bias, which will be considered in the interpretation of the results. The discussion will highlight the similarities and differences in the findings to provide context for the study's outcomes. Additionally, the Clinical Study Report will include a description of the methodology utilized, including search keywords, inclusion and exclusion criteria for relevant studies, and data collection form used in the analysis.

Statistical Analysis Plan (SAP) will be developed subsequently to the protocol. The SAP will be finalized prior to database lock to ensure the integrity of the analysis. It will outline detailed statistical methods, including but not limited to, the statistical models to be used for comparative analyses, the handling of missing data, and the approach for subgroup analyses. The SAP will also specify the statistical software to be used for these analyses.

10.8 QUALITY CONTROL

The study will be conducted according to the protocol and in compliance with relevant regulations and guidelines (ICH-GCP and local law). Any modifications to the protocol must be approved by the study principal investigator and the study Sponsor. These revisions will be properly documented as protocol amendments and shared with ethics committees and study sites. After finalizing the protocol amendments, they will be submitted to the Ethics Committee, Office for Registration of Medicinal Products, Medical Devices and Biocides (URPL) and the European Medicines Agency (EMA) for approval.

Corza Medical will act as the database holder for the retrieved data and will also be responsible for securely storing and eventually destroying the data after the study concludes. The study will adhere to the standard operating procedures established by Corza Medical or an entity involved in conducting the study. These procedures encompass internal quality audits, secure and confidential data storage practices, document archiving methods, programming quality control procedures, standards for writing analysis plans, and the requirement for senior scientific review.

All work conducted will be subjected to rigorous quality control and documentation procedures to ensure accuracy and thoroughness in the final report, as well as reproducibility of the analyses. If the data do not allow for the planned analysis or if additional analyses are needed, the report(s) will include any missing or supplementary information along with the corresponding explanations. Key study documents such as the protocol, statistical analysis plan, and study reports will undergo quality control review, senior scientific review, and editorial review.

A quality control process will be implemented to ensure the accuracy and completeness of data collected in the electronic Case Report Form (eCRF) and data collected by the Sponsor during the literature review process. In terms of data collected in the eCRF, this process will involve verifying that all mandatory variables are collected and performing cross-checks for data consistency and correctness by the Data Management team. Any discrepancies, missing data, or errors identified within the eCRF data will be verified and resolved in collaboration with the site or Investigator. For data collected outside the eCRF and managed directly by the Sponsor, a parallel quality control process will be applied. If any required information is found

PasTel

to be missing or incorrect, the Biostatistician will coordinate directly with the Sponsor to secure the necessary corrections or additional data.

These measures ensure that all data, regardless of its source, adheres to the study's quality and completeness standards.

The programs for Data Management and Statistics will be developed by the Data Manager(s) and Biostatistician(s), with independent quality control checks conducted by another Data Manager and Biostatistician to ensure accuracy. All processes related to Data Management and Statistics leading to the dissemination of study results will undergo rigorous quality control checks, including verification of programs, result tables, and written text. These checks will be documented in accordance with the CRO's Standard Operating Procedures (SOPs).

10.9 LIMITATIONS OF THE RESEARCH METHODS

One of the strengths of PasTel study is a prospective observational study design, which allows for the collection of data over time. This design is suitable for examining the short- and long-term safety of TachoSil application and can provide valuable insights into the outcomes of the treatment. The study is an observational cohort study, which means that it does not involve any interventions or experimental procedures. This design allows for the examination of the treatment's safety in a real-world setting, reflecting the routine clinical practice. The study aims to recruit a substantial number of patients, which can enhance the generalizability of the findings and provide more robust results. The study includes a specific population of paediatric patients undergoing cardiovascular, hepatic, or other solid organ surgeries, as well as polytrauma with certain injuries. This targeted approach ensures that the study focuses on patients who are likely to benefit from TachoSil application, allowing for a more accurate assessment of its safety in the intended population. Additionally, the PasTel study follows patients up to 36 months after surgery, enabling the examination of both short- and long-term safety outcomes. This duration allows for the identification of potential adverse events or complications that may occur over an extended period.

Despite these strengths, PasTel study has also some limitations. The study does not include a control group for comparison. Without a control group receiving an alternative treatment or a placebo, it may be challenging to attribute observed outcomes solely to the TachoSil application. The absence of a control group limits the ability to establish causality or make direct comparisons. PasTel study relies on patient self-reporting during follow-up visits, which may introduce recall bias or incomplete data. Depending on the method of follow-up (in-person or telephone visits), the accuracy and reliability of the information collected may vary. Confounding by indication is also very common in observational studies (e.g., cohort studies). It can occur in relation to either beneficial outcomes or harmful outcomes and can result in either an increase or a reduction in the apparent risk of the outcome. However, careful study design, e.g., including a range of different indications for the same exposures, enables the relationship between the exposure and the outcome in relation to each of the individual indications to be analysed separately. A consistent outcome across all indications will suggest that the outcome is indeed due to the exposure, since it is unlikely that each different indication would cause the same outcome.

The study design may be prone to selection bias, primarily due to its non-interventional, observational nature and specific inclusion/exclusion criteria. By focusing only on paediatric patients undergoing certain types of surgery and requiring specific haemostatic treatments, the study might not represent the broader paediatric population undergoing various surgical

PasTel

procedures. Additionally, excluding patients with congenital disorders of haemostasis or severe coagulopathy could further skew the results, as these patients might exhibit different safety profiles or adverse event rates. These selective criteria can impact the generalizability of the study findings to all paediatric surgical patients.

Finally, participants have the option to withdraw from the study at any time, which could lead to attrition bias if those who withdraw differ systematically from those who remain. Additionally, discontinuation may result in incomplete data for some patients, potentially affecting the overall study findings.

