80.7% 95% CI, 72.3 – 87.5	87.5% 95% CI, 47.3 – 99.7	85% 95% CI, 62.1 – 96.8	81.3% 95% CI, 61.8 – 100.0

The applicant furthermore provided a pooled analysis based on the paediatric patients from the above two mentioned studies TC-019-IN and TC-2402-040-SP. A total of 45 paediatric subjects were included in the paediatric study pool: 36 in the TachoSil group (8 randomised and 12 from the extension part from study TC-2402-040-SP, as well as 16 patients enrolled in TC-019-IN) and 9 in the comparator group (from study TC-2402-040-SP, all randomised).

The majority of subjects in both treatment groups experienced TEAEs that were considered mild or moderate in intensity, all of which were considered not related to study treatment. Incidence of severe adverse events was approximately the same across treatment groups and only 20 of 272 total adverse events were considered severe.

SAEs were reported by 17 of 36 subjects in the TachoSil group and 4 of 9 subjects in the Comparator group. No subjects in either treatment group experienced an SAE that was considered related to study treatment.

Events of special interest were presented for the paediatric study pool in comparison to the comparator Surgicel. More thrombotic/embolic events and postoperative bleedings were seen in the TachoSil-group. Tissue adhesions were similar. Immunogenicity testing and viral serology was not performed in paediatric subjects up to 6 months of age, nor for subjects enrolled in the paediatric extension part. Immunogenicity was tested in 2 children treated with TachoSil and 2 children treated with Surgicel. Only 1 paediatric subject had a 1-month follow-up test, which was negative for antibodies.

PasTel

Table 4 Overall Summary of subjects with events of special interests by treatment studies TC-2402-040-SP and TC-019-IN, paediatric population

Medical Category	TachoSil N=36 n (%)	Comparator N=9 n (%)	Total N=45 n (%)
Thrombotic and embolic events	2 (5.6)	0	2 (4.4)
SAEs	2 (5.6)	0	2 (4.4)
Postoperative bleeding at surgical site	16 (44.4)	3 (33.3)	19 (42.2)
SAEs	5 (13.9)	0	5 (11.1)
Immunological events	4 (11.1)	1 (11.1)	5 (11.1)
SAEs	1 (2.8)	0	1 (2.2)
Abscess and other surgical related infections	2 (5.6)	3 (33.3)	5 (11.1)
SAEs	0	1 (11.1)	1 (2.2)
Tissue adhesions	8 (22.2)	2 (22.2)	10 (22.2)
SAEs	4 (11.1)	1 (11.1)	5 (11.1)

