10. RESEARCH METHODS

10.1 STUDY DESIGN

This is a prospective, multicentre, non-interventional, uncontrolled, observational, post-authorization cohort study aimed at investigating the short- and long-term safety of TachoSil application.

The study will enrol patients undergoing cardiovascular, hepatic or other solid organs surgery, as well as those with injuries of blood vessels, parenchymal organs, lungs requiring the use of drugs for local haemostasis, tissue sealing, and suture support in vascular surgery where standard techniques are insufficient and where TachoSil was used as a secondary haemostatic treatment. The cohort will include patients identified by participating investigators (prospective enrolment). Patients who meet specified inclusion/exclusion criteria and their legal representatives will receive comprehensive information about the study orally and in written form, tailored to their understanding. The investigator will obtain their voluntary, personally signed, and dated informed consent before collecting any study-related information.

Short-term safety data, including adverse events (AEs) and adverse events of special interest (AESIs), will be collected prospectively from the time of informed consent signature, during hospital stay, and until hospital discharge. Time to onset (TTO), duration, severity, outcome, treatment and relatedness to TachoSil will be analyzed for reported AEs and AESI.

All enrolled patients will be followed for up to 36 months after surgery to monitor long-term treatment-related events and their clinically significant consequences.

To minimize stress for patients and caregivers associated with the study and the surgical intervention itself, the number and frequency of follow-up visits during the observation period will align with the routine follow-up procedures of the clinical sites.

Primary endpoint:

1. The proportion of subjects experiencing clinically significant local reactions including abscesses, hematoma formation or foreign body granuloma formulation, at the site of TachoSil application from the start of surgery up to 36 months post-surgery, as detected through routine imaging examinations (X-ray, ultrasound, CT, MRI or intraoperative detection or physical examination).

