TachoSil is a fibrin sealant and has the same action despite the indication (type of surgery) for which it is used. Effect modification is all about stratification and occurs when an exposure has a different effect among different subgroups. Therefore, effect modifiers are not relevant for this study.

Section 9: Data sources		Yes	No	N/A	Section Number
9.1	Does the protocol describe the data source(s) used in the study for the ascertainment of:				
9.1.1	Exposure? (e.g. pharmacy dispensing, general practice prescribing, claims data, self-report, face-to-face interview)				9.3
9.1.2	Outcomes? (e.g. clinical records, laboratory markers or values, claims data, self-report, patient interview including scales and questionnaires, vital statistics)				9.3
9.1.3	Covariates and other characteristics?				9.3
9.2	Does the protocol describe the information available from the data source(s) on:				
9.2.1	Exposure? (e.g. date of dispensing, drug quantity, dose, number of days of supply prescription, daily dosage, prescriber)				9.3
9.2.2	Outcomes? (e.g. date of occurrence, multiple events, severity measures related to event)				9.3
9.2.3	Covariates and other characteristics? (e.g. age, sex, clinical and drug use history, co-morbidity, co-medications, lifestyle)				9.3
9.3	Is a coding system described for:				
9.3.1	Exposure? (e.g. WHO Drug Dictionary, Anatomical Therapeutic Chemical (ATC) Classification System)				9.3
9.3.2	Outcomes? (e.g. International Classification of Diseases (ICD), Medical Dictionary for Regulatory Activities (MedDRA))				9.3
9.3.3	Covariates and other characteristics?				9.3

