9.4	Is a linkage method between data sources described? (e.g. based on a unique identifier or other)				9.6

Comments:

It should be noted that information available from data sources (medical records maintained at site) is to be determined after completion of feasibility questionnaires by all Investigators. At the time of filling this checklist, feasibility evaluation was not completed.

Section 10: Analysis plan		Yes	No	N/A	Section Number
10.1	Are the statistical methods and the reason for their choice described?				9.7
10.2	Is study size and/or statistical precision estimated?				9.7
10.3	Are descriptive analyses included?				9.7
10.4	Are stratified analyses included?				9.7
10.5	Does the plan describe methods for analytic control of confounding?				9.7
10.6	Does the plan describe methods for analytic control of outcome misclassification?				9.7

PasTel

Section 10: Analysis plan	Yes	No	N/A	Section Number
10.7 Does the plan describe methods for handling missing data?				9.7
10.8 Are relevant sensitivity analyses described?				9.7

Comments:

Analysis plan is briefly described and includes simple descriptive statistics for evaluation of adverse events of TachoSil use. Final version of analysis plan will be determined after completion of feasibility questionnaires by all Investigators. At the time of filling this checklist, feasibility evaluation was not completed.

Section 11: Data management and quality control	Yes	No	N/A	Section Number
11.1 Does the protocol provide information on data storage? (e.g. software and IT environment, database maintenance and anti-fraud protection, archiving)				

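### Section 10.9 reads similar outcomes across indications as pointing to TachoSil, but where every child has both surgery and TachoSil they cannot separate product from surgery

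*Protocol*

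**What the plan says.** Section 10.1 describes a "prospective, multicentre, non-interventional, uncontrolled, observational, post-authorization cohort study". Section 10.7 defines the analysed population as "all enrolled subjects who received at least 1 application of TachoSil".

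Section 10.9 first concedes the consequence: "The absence of a control group limits the ability to establish causality or make direct comparisons". The same paragraph then raises confounding by indication and offers an answer. Covering several indications is said to allow the exposure-outcome relationship to be examined in each one separately, and then: "A consistent outcome across all indications will suggest that the outcome is indeed due to the exposure". The reason given is "since it is unlikely that each different indication would cause the same outcome".

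The ENCePP checklist in Annex 2 bears on this in three places:
- Item 7.1, on confounding, is ticked Yes with a reference to 9.9. That appears to mean the present section 10.9, because the checklist's section numbers run one behind the protocol's.
- Item 10.4 ("Are stratified analyses included") is ticked No, as is item 10.5 on analytic control of confounding.
- Item 8.1 is ticked not applicable, with the comment "Therefore, effect modifiers are not relevant for this study".

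**The concern.** Consistency across indications helps a causal argument only when each indication supplies its own comparison of exposed with unexposed patients, and those comparisons agree. Here no indication supplies one.

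The reason offered also fails. It assumes that the indications have no common cause of the outcome, yet all of them involve surgery, and section 10.2 adds bleeding for which standard techniques were ineffective or impractical. Either is a plausible route to haematoma, infection, re-bleeding or adhesions whatever the indication.

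The stake is the interpretation of a safety study that goes to the EMA. A report that followed the sentence could present ordinary surgical complications, seen at similar rates in cardiovascular, hepatic and trauma patients, as effects of the product. It is also the only answer to confounding by indication that section 10.9 gives.

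**Working it through.** **What the design identifies.** For indication k, let `b_k` be the risk from surgery and underlying disease without TachoSil, and `d_k` the part added by TachoSil. All analysed children are exposed, so only the sum is observed:

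`r_k = b_k + d_k`

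With K indications there are K observed rates and 2K unknowns. A consistent outcome means that all `r_k` are about equal. If each is 22.2%, then `b_k = 22.2%, d_k = 0` fits exactly as well as `b_k = 0, d_k = 22.2%`. The data cannot choose between them.

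**Is there an unexposed group anywhere?** Section 10.5 says all patients who undergo surgery are analysed, but section 10.7 restricts every analysis to those with at least one TachoSil application. No unexposed comparison group is defined.

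**The protocol's own background.** Section 8 (Rationale) says TachoSil safety data generally reflect post-operative complications of the surgical setting and the underlying disease. That is the common cause which section 10.9 treats as unlikely. In Table 4, adhesions occurred in 8/36 = 22.2% with TachoSil and 2/9 = 22.2% with comparator ("Tissue adhesions were similar"), and postoperative bleeding in 16/36 = 44.4% and 3/9 = 33.3%. These counts show only that such outcomes also occur without TachoSil.

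**Study size.** Section 10.2 gives 66 recruited, 10% dropout and at least 60 for analysis. 66 × (1 − 0.10) = 59.4, so about 60; the stated figure reproduces.

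**How easily would strata look consistent?** The protocol gives no split by indication, so equal strata are an assumption here.
- Four strata: 60/4 = 15. With 3/15 events (20%), the exact (Clopper-Pearson) 95% CI is 4.3% to 48.1%.
- Three strata: 60/3 = 20. With 4/20 events (20%), it is 5.7% to 43.7%; with 0/20 the upper limit is 16.8%.

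The next table gives the proportion of simulated studies (40,000 runs each) with **no product effect** in which a chi-square homogeneity test gave p > 0.05:

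| Strata | True background risks | Look consistent |
|---|---|---|
| 3 × 20 | 22.2% in all | 95% |
| 3 × 20 | 5.6% in all | 97% |
| 3 × 20 | 15%, 22.2%, 30% | 84% |
| 3 × 20 | 10%, 22.2%, 35% | 62% |
| 4 × 15 | 22.2% in all | 95% |
| 4 × 15 | 10%, 20%, 25%, 35% | 76% |

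In every row the true product effect is zero, yet most studies would meet a condition that section 10.9 reads as suggesting a product effect.

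**The case against.** The best defence is that this is a sentence of discussion, not an analysis. Section 10.7 plans descriptive proportions, cumulative incidence and a qualitative literature comparison. No hypothesis is tested. Relatedness is judged event by event under section 12, not by comparing indications. The text says only that consistency will suggest causation, and the caveat about the missing control group stands a few sentences earlier. All of this is true. It limits the harm to interpretation, but it does not make the inference valid, and the caveat is what the sentence then undoes.

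A second defence is that size and number of patches (section 10.3) vary within an indication, which gives some exposure contrast. The sentence does not invoke dose, however, and the amount used may itself follow wound size and bleeding, so it would not remove the confounding.

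Some stronger readings are tempting but unsupported:
- **That the protocol claims proof, or that the report would certainly misattribute events.** It says suggest; misattribution is a possibility.
- **That differing rates would be taken to clear the product.** Section 10.9 says nothing about inconsistent outcomes.
- **That Table 4 refutes the rule or shows TachoSil does not cause adhesions.** Both pooled studies were in hepatic surgery, so the table covers one indication and cannot test consistency across several. The comparator was an active haemostatic in nine children; for 2/9 the exact 95% CI is 2.8% to 60.0%.
- **That strata will nearly always look consistent.** About 95% applies only when background risks are equal.
- **That no analysis by indication will be done.** Section 10.7 leaves the subgroup approach to the SAP, and the checklist comment calls the analysis plan provisional. The checklist answers show a mismatch with section 10.9, not a settled omission.

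**Conclusion.** The concern holds as a fault in stated reasoning. In a single-arm cohort where every analysed child has surgery and TachoSil, agreement across indications cannot support attribution to the product, and section 10.9 should not say that it does. The sentence conflicts with the caveat in its own paragraph. It also leans on analysis by indication that checklist item 10.4 marks as not included and on stratification that item 8.1 dismisses as irrelevant.

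This conclusion rests on the design alone (uncontrolled, all exposed, shared surgery) and needs no numerical assumption. The interval and simulation figures are illustrations that assume equal strata and the background risks shown. No endpoint or planned estimate changes; what changes is what the final report may conclude.

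**What to change.** In section 10.9, delete the two sentences that close the discussion of confounding by indication: the one presenting a range of indications as a design remedy, and the one on consistent outcomes. Replace them with:

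> All children undergo surgery and receive TachoSil, so similar or different rates across indications cannot distinguish a product effect from a surgical or underlying-disease effect. Any results by type of surgery are descriptive, and no causal conclusion will be drawn from consistency across indications.

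Align the checklist with this: item 7.1 should no longer rest on the deleted argument, and items 8.1 and 10.4 should agree with whatever description by type of surgery is intended. Do not print the Table 4 comparator rates beside PasTel rates. They come from nine children in hepatic surgery, while PasTel covers other surgery, counts only clinically significant adhesions and follows children for 36 months.

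The cost is wording. Type of surgery is already collected (section 10.3), so no new data are needed. Because section 10.8 sends amendments for approval, the change can go with the next one.
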